2.4 Sample Size

The sample size of 1,500 subjects is necessary based on advice from the United States Food and Drug Administration US FDA requesting that 1,000 preterm infants be exposed to MEDI8897 in this Phase 2b study. This sample size has approximately > 99% power to detect 70% relative-risk reduction, assuming a placebo group medically attended RSV LRTI incidence of 8%. Power calculations are based on a Poisson regression model with robust variance (Zou, 2004) comparing MEDI8897 50 mg versus placebo, with 2-sided, $\alpha = 0.05$.

- The 70% relative-risk reduction assumption is based on a placebo-controlled study in Native American infants in which there was 87% relative reduction in the incidence of RSV hospitalization (11.3% placebo; 1.5% motavizumab; $p < 0.001$) and 71% relative reduction in the incidence of outpatient RSV LRTI (10.0% placebo; 2.9% motavizumab; $p < 0.001$) in infants who received motavizumab prophylaxis (O'Brien et al, 2015)

In order to evaluate risk, a sample size of 1,000 subjects exposed to MEDI8897 will provide a 90% probability of observing at least one AE if the true event rate is 0.2%; if no AEs are observed, this study provides 95% confidence that the true event rate is < 0.3%.

3 STATISTICAL METHODS

3.1 General Considerations

Summary statistics will be tabulated by treatment group. Categorical data will be summarized by the number and percentage of subjects in each category. Continuous variables will be summarized by mean, median, standard deviation, minimum, and maximum. In general, unless stated otherwise, baseline will be defined as the last non-missing value prior to dosing.

There are two planned analyses for this study: the Primary Analysis and the Final Analysis. The Primary Analysis will be conducted after all randomized subjects have completed the Day 151 visit. At the time of this primary analysis, approximately half of all subjects enrolled (722 subjects) will have completed the Day 361 visit. The remaining 731 subjects will have completed approximately 8 months of the study. MEDI8897’s efficacy will be evaluated in the Primary Analysis as intended by the study design. In addition, all available PK, ADA, and safety data will be analyzed. The final analysis will be conducted when all subjects have completed the last visit of the study.

Data analyses will be conducted using the SAS® System Version 9.3 or higher (SAS Institute Inc., Cary, NC) in a SAS GRID environment.

3.2 Analysis Populations and Datasets

The analysis populations are defined in [Table 3.2-1](#).

Table 3.2-1 Analysis Populations

Population	Description
Intent-to-treat (ITT) population	Subjects who are randomized will be included in the ITT population; in this population data will be analyzed according to their randomized treatment group.
As-treated population	Subjects who are randomized and receive any study investigational product will be included in the as-treated population; in this population, data will be analyzed according to the treatment they actually receive.
Per-protocol population	The per-protocol population includes subjects in the ITT population who receive the correct dose of randomized treatment and who do not have a serious protocol violation. Detailed criteria defining this population will be determined and documented prior to performing the Primary Analysis.

Analysis Datasets

- The Primary Dataset contains all data (efficacy, safety, ADA, PK) from all randomized subjects through the Day 151 visit and all available safety data as of the data cutoff date. The Primary Analysis will be performed on the Primary Dataset.
- The Final Dataset contains all data collected in this study, including data in the Primary Dataset and data from the subjects who were ongoing at the time when the Primary Dataset was locked. The Final Analysis will be performed on the Final Dataset.

3.3 Stratification Factors

Two stratification factors are used in study design as well as in data analysis, and these are: age group at randomization [age \leq 3 months (ie, age \leq 91 days), age $>$ 3 to \leq 6 months (ie, age $>$ 91 to \leq 183 days), age $>$ 6 months (ie, age $>$ 183 days)] and hemisphere (northern hemisphere, southern hemisphere). For subjects who were assigned to an incorrect age stratum at randomization, the age stratum as calculated from the electronic case report form (eCRF) will differ from the stratum recorded for the subject in the IWRS database. Unless stated otherwise, the age stratum based on the CRF calculation will be used.

CRF calculation for age when full date of birth (DOB) is available:

- Age at randomization (months) = (randomization date – DOB) / (365.25/12)

When full DOB is unavailable, age at screening will be used. Since screening may be collected in terms of days, weeks, or months, it will be first converted in terms of months as follows:

- Age at screening (days) / (365.25/12) = Age at screening (months)
- Age at screening (weeks) / (52/12) = Age at screening (months)

Once age at screening is converted to months,

- Age at randomization (months) = Age at screening (months) + [(randomization date – screening date) / (365.25/12)]

Determination of hemisphere in stratification and analysis is as follows: The sites have been grouped together by country into the following two hemispheres: Northern Hemisphere (Belgium, Bulgaria, Canada, Czech Republic, Estonia, Finland, France, Hungary, Italy, Latvia, Lithuania, Poland, Spain, Sweden, Turkey, United Kingdom, and United States of America [USA]) and Southern Hemisphere (Argentina, Australia, Brazil, Chile, New Zealand, and South Africa).

3.4 Study Subjects

3.4.1 Subject Disposition and Completion Status

A summary of subject eligibility and randomization as well as treatment received (including summary of subjects randomized but not treated) will be provided. In addition, disposition of subjects throughout the study and by visit will be provided. This summary will be presented

by treatment group and for all subjects combined. The denominators for this summary will include all subjects who were randomized into the study.

3.4.2 Demographics and Baseline Characteristics

Enrolment will be summarized by hemisphere, country, site, and by hemisphere, country, and age at randomization stratum for each treatment group and for all subjects combined. The total number of subjects randomized into each treatment group will be used as the denominator. For the summary of hemisphere, country, and age at randomization stratum, the number of mis-stratified subjects (ie, age stratum as calculated from the eCRF does not match the IWRS database) will be summarized.

Demographic information related to gender, age at randomization (months) calculated from the CRF, age at randomization category determined using the CRF age calculation (age \leq 3 months, age $>$ 3 to \leq 6 months, age $>$ 6 months), GA (weeks), GA category (29-32 weeks, $>$ 32 weeks), ethnicity, race, weight (kg) on day 1, weight on day 1 category (weight \leq 2.5 kg, weight $>$ 2.5 to \leq 5 kg, weight $>$ 5 kg), birth weight (kg), birth weight category (weight \leq 2.5 kg, weight $>$ 2.5 kg), multiple birth (yes/no), and siblings enrolled in the study (yes/no) will be summarized by treatment group and for all subjects combined using the ITT population. Subjects will be excluded from the summary (eg, means and percentages) of an individual parameter if data are missing. This will be done for all subjects, each age category at randomization, country, and by hemisphere.

3.4.3 Study Drug Exposure

Due to the simplicity of dosing for this study, exposure is summarized in the Subject Disposition and Completion Status table under “Randomized and dosed.” No other summary will be reported.

3.5 Efficacy Analyses

The analyses of the primary efficacy endpoint, the protocol-defined medically attended RSV LRTI through 150 days post dose (also described as the medically attended RSV LRTI through 150 days post dose in Section 3.5.1., Primary Efficacy Endpoint and Analyses), and the secondary efficacy endpoint, the protocol-defined RSV hospitalization through 150 days post dose (also described as the RSV LRTI hospitalization in Section 3.5.2., Secondary Efficacy Endpoint and Analyses), will be performed on the Primary Dataset.

The Final Dataset will include the events that occurred 150 days post dose, either medically attended RSV LRTI or RSV hospitalization, therefore will be used to summarize these events

that occurred after Day 151 or up to Day 361. Efficacy analyses performed on the Primary Dataset will be refreshed in the Final Dataset to make sure statistical inferences on MEDI8897 efficacy made from the Primary Analysis are consistent with those from the Final Dataset.

3.5.1 Primary Efficacy Endpoint and Analyses

3.5.1.1 Primary Efficacy Endpoint

The primary endpoint is the incidence of medically attended RSV LRTI (inpatient and outpatient) through 150 days post dose. For subjects with multiple medically attended RSV LRTI events (inpatient or outpatient), only the first occurrence will be used in the primary analysis.

The determination of medically attended RSV LRTI will be based on objective clinical LRTI criteria (described in the Protocol [Section 4.3.1.1](#) and SAP [Appendix 1](#)) and RSV test results obtained from analyzing the respiratory secretions using a validated RSV RT-PCR assay for the detection of RSV A or RSV B performed in a central laboratory. These LRTI events may occur in the inpatient or outpatient visit setting.

Prior to database lock for the primary analysis, a blinded review of data will be undertaken to determine an analysis window such that all positive results will be counted as a medically attended RSV LRTI if they occurred in a respiratory sample collected within this window relative to the initial date seen by the healthcare provider (eg, admission/deterioration date associated with the event, urgent care visit, outpatient ED visit, or outpatient clinic visit). The actual window used will be documented prior to unblinding. In addition, deaths that can be demonstrated as caused by RSV (by autopsy or clinical history and virologic evidence) will also be considered as primary medically attended RSV LRTI events.

3.5.1.2 Primary Efficacy Analysis

The primary efficacy analysis of the primary endpoint will be performed on the ITT Population. A Poisson regression model with robust variance ([Zou, 2004](#)) will be used as the primary efficacy analysis model to estimate the relative risk on the incidence of medically attended RSV LRTI between the MEDI8897 and the placebo groups. The model contains the term of treatment group and age group at randomization based on the calculation detailed in Section 3.3. (ie, age ≤ 3 months, age > 3 to ≤ 6 months, age > 6 months) and dichotomous temperate (northern and southern) hemispheres as covariates. The relative risk reduction, defined as $1 - \text{Relative Risk (RR)}$, and its corresponding 2-sided 95% CI, will be estimated from the model. In addition, the 2-sided p-value testing null hypothesis that the incidence of

medically attended RSV LRTI between MEDI8897 and placebo groups are the same will be obtained from the model. Statistical significance will be achieved if the 2-sided p-value is ≤ 0.05 .

The Poisson regression with robust variance analysis will be implemented by using the SAS PROC GENMOD procedure with the REPEATED statement for subject ID and logarithm link. The estimated parameter $\hat{\beta}$ [ie, $\log(\widehat{RR})$], 2-sided 95% confidence interval (CI) for $\hat{\beta}$, and the 2-sided p-value will be obtained from the SAS outputs. The estimated RR and corresponding CI for the RR is given by exponentiating $\hat{\beta}$ and its confidence limits. Therefore, the percent of RR reduction is given by $[(1 - \exp(\hat{\beta})) * 100\%]$. The CI for the percent of RR reduction is given by $([1 - \exp(\text{upper confidence limit for } \hat{\beta}) * 100\%], [1 - \exp(\text{lower confidence limit for } \hat{\beta}) * 100\%])$.

If the number of subjects in any stratum is too small and/or convergence cannot be achieved with the Poisson regression analysis model, the stratified Cochran-Mantel-Haenszel (CMH) test (detailed in Section 3.5.1.4) will be used as the primary analysis model to test the treatment effect on medically attended RSV LRTI between MEDI8897 and placebo groups.

The above described analysis on the primary efficacy endpoint will also be conducted on the Per-protocol population.

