4 MATERIALS AND METHODS

4.1 Subjects

4.1.1 Number of Subjects

A total of 1,500 infants will be enrolled and randomized in a 2:1 ratio to receive a single IM dose of ■ mg MEDI8897 (N = 1000) or placebo (N = 500).

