4.8.2 Sample Size and Power Calculations

The sample size of 1,500 is necessary based on advice from the US FDA requesting that 1,000 preterm infants be exposed to MEDI8897 in this Phase 2b study. This sample size has approximately 99% power to detect 70% relative risk reduction, assuming a placebo group medically attended RSV LRTI incidence of 8%. Power calculations are based on Poisson

regression model with robust variance (Zou, 2004) comparing MEDI8897 [REDACTED] mg versus placebo, with 2-sided significance level of $\alpha = 0.05$.

- The 70% relative risk reduction assumption is based on a placebo-controlled study in Native American infants in which there was 87% relative reduction in the incidence of RSV hospitalization (11.3% placebo; 1.5% motavizumab; $p < 0.001$) and 71% relative reduction in the incidence of outpatient RSV LRTI (10.0% placebo; 2.9% motavizumab; $p < 0.001$) in infants who received motavizumab prophylaxis (O'Brien et al, 2015)

In order to evaluate risk, a sample size of 1,000 subjects exposed to MEDI8897 will provide a 90% probability of observing at least one AE if the true event rate is 0.2%; if no AEs are observed, this study provides 95% confidence that the true event rate is $< 0.3\%$.

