4.8.3.1 Primary Efficacy Analysis

The incidence of RSV LRTI (inpatient and outpatient) during 5 months of the RSV season will be based on RSV test results (performed centrally via RT-PCR) and objective clinical LRTI criteria and will be summarized by treatment group. For subjects with multiple medically attended RSV LRTI events, only the first occurrence will be used in the primary analysis.

The primary efficacy analysis of the primary endpoint will be conducted with the ITT Population. LRTI caused by RSV that occurs prior to discontinuation from participation in the study will contribute to the primary efficacy analysis. For subjects who do not have an RSV LRTI prior to discontinuation from participation, their event status will be imputed assuming the observed placebo RSV LRTI rate. This will be implemented by imputations based on repeated simulations and will be described in the Statistical Analysis Plan. A Poisson regression model with robust variance (Zou, 2004) will be used as the primary

efficacy analysis model to compare the incidence of medically attended RSV LRTI between MEDI8897 and placebo, including treatment group, age at the time of randomization (ie, ≤ 3 months, $> 3 - \leq 6$ months, > 6 months) and dichotomous temperate (northern and southern) hemispheres as covariates. In addition, the 2-sided p-value and corresponding 2-sided 95.1% CI on the relative risk will be provided from the model. Relative risk reduction is defined as $(1 - P_n/P_s)$ where P_n is the incidence of RSV LRTI during 5 months of the RSV season in the MEDI8897 group and P_s is the incidence of RSV LRTI during 5 months of the RSV season in the placebo group generated from the model. Statistical significance will be achieved if the 2-sided p-value is ≤ 0.05 .

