3.5.1.4 Additional Analyses of the Primary Efficacy Endpoint

The following analyses will be conducted on the ITT population.

To allow for differences in follow-up time, the primary analysis using a Poisson Regression with robust variance will be repeated, adjusting for the same covariates as well as log (follow-up time) as an offset. Since the follow-up time is adjusted in the model, there is no missing imputation for this analysis. Calculation of follow-up are detailed as follows:

- For subjects who meet the medically attended RSV LRTI endpoint within 150 days post dose, the follow-up time will be calculated as (Date of Onset of RSV LRTI) – (Date of Dosing) +1.
- For subjects who do not experience a medically attended RSV LRTI event within 150 days post dose, the efficacy follow-up will be determined based on the following:
 - If an end of study date occurs within 150 days post dose (or end of study date is missing and last assessment date occurs within 150 days post dose), the efficacy follow-up will be calculated as (Date of End of Study or Date of Last Assessment, whichever is later) – (Date of Dosing) +1.

- If an end of study date occurs after 150 days post dose (or end of study date is missing and last assessment date is after 150 days post dose), the efficacy follow-up will be censored (at 151 days).

A CMH test stratified by hemisphere and age group at randomization (ie, age ≤ 3 months, age > 3 to ≤ 6 months, age > 6 months) will be used to compare between treatment groups through 150 days post dose as the key secondary analysis for the primary endpoint. SAS procedure of PROC FREQ with CMH option will be used to perform the analysis. The relative risk of MEDI8897 over placebo for the incidence of medically attended RSV LRTI events and the 95% CI will be obtained from the SAS procedure. The percent of RR reduction and the 95% CI will be reported following the relationship of RR reduction (%) = $(1 - \text{relative risk}) * 100\%$. This analysis will be performed without any imputation of event for MEDI9987 subjects who dropped out the study prior to Day 150 post dose and did not have a medically attended RSV event.

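### The fallback CMH primary analysis drops the placebo-rate imputation that the primary analysis requires, and one of its two triggers has no threshold

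*SAP*

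**What the plan says.** The current plan is SAP version 5, read with Protocol Amendment 1.

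- **Primary rule in the protocol (4.8.3.1).** For infants who leave the study without an RSV LRTI, "their event status will be imputed assuming the observed placebo RSV LRTI rate". Section 4.8.3.2 gives the CMH test only the role of a sensitivity analysis. The protocol has no fallback for the primary model.
- **Primary rule in the SAP (3.5.1.3).** Missing outcomes in the primary analysis are imputed by stratum at the placebo rate. The Poisson model is fitted to 20 completed datasets and the results are pooled.
- **Fallback (SAP 3.5.1.2).** "If the number of subjects in any stratum is too small and/or convergence cannot be achieved with the Poisson regression analysis model", the stratified CMH test becomes the primary analysis model. The reader is sent to 3.5.1.4 for its details.
- **The CMH test itself (SAP 3.5.1.4).** "This analysis will be performed without any imputation of event for MEDI9987 subjects who dropped out the study prior to Day 150 post dose". MEDI9987 is evidently a misprint for MEDI8897.

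SAP version 4 had the same fallback sentence, but its CMH test was run on placebo-rate-imputed data. The log relative risk was pooled through MIANALYZE and the p-value through a Wilson-Hilferty transformation. Version 5 removed the imputation and left the fallback sentence as it was. The change between versions is not itself an error; the fault is that the remaining version 5 sections disagree with each other and with the protocol.

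**The concern.** If the fallback is used as written, the pivotal p-value and efficacy estimate come from an analysis without the protocol's deliberately conservative treatment of dropouts. The same p-value decides whether RSV hospitalization may be tested (SAP 3.5.2.2).

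The stratum trigger is also loose. It has no minimum size, no time of assessment and no named decision-maker. Its and/or wording lets a small stratum force the switch even when the Poisson model converges. That model has main effects only: intercept, treatment, two age terms and one hemisphere term, five parameters in all. One sparse cell among the 2 × 3 = 6 strata does not by itself make it fail. By contrast, 3.5.1.1 requires the sampling window to be set in a blinded review and documented before unblinding.

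**Working it through.** **Inputs.** Protocol 4.1.1: "A total of 1,500 infants will be enrolled and randomized in a 2:1 ratio", that is 1,000 and 500. Protocol 4.8.2: "approximately 99% power to detect 70% relative risk reduction", with placebo incidence 8% and two-sided alpha 0.05. SAP 3.5.1.1 sets the endpoint at 150 days. SAP 3.1 gives 722 + 731 = 1,453 enrolled; a 2:1 split is about 969 and 484. No dropout rate is given, so 3%, 5% and 10% are assumed.

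**The plan's own figure.** MEDI8897 risk = 0.30 × 8% = 2.4%. The standard error of the log relative risk is √(0.976/24 + 0.92/40) = 0.2523. Then |ln 0.30| / 0.2523 = 4.77, and Φ(4.77 − 1.96) = 99.75%. A pooled two-proportion calculation gives 99.57%. The stated power is reproduced.

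**Effect of the missing-data rule.** Let r be the relative risk among infants followed, and dM and dP the shares of event-free dropouts on MEDI8897 and placebo.

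- Imputed at the placebo rate: RR = (1 − dM)·r + dM
- Not imputed, dropouts kept as non-events: RR = r·(1 − dM)/(1 − dP)

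With r = 0.30 and equal dropout:

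| Dropout | Imputed RR | Imputed RRR | Unimputed RRR |
|---|---|---|---|
| 3% | 0.97 × 0.30 + 0.03 = 0.321 | 67.9% | 70.0% |
| 5% | 0.95 × 0.30 + 0.05 = 0.335 | 66.5% | 70.0% |
| 10% | 0.90 × 0.30 + 0.10 = 0.370 | 63.0% | 70.0% |

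Version 5 does not say whether unimputed dropouts stay in as non-events or are excluded. With equal dropout, both readings give 70.0%.

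**Confidence limit at 10% dropout, 969 and 484.** Variance per arm is (1 − p)/(np), ignoring between-imputation variance.

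- Imputed: risks 2.96% and 8%, SE 0.240, lower limit 1 − 0.37·exp(1.96 × 0.240) = 40.8%.
- Unimputed: risks 2.16% and 7.2%, SE 0.271, lower limit 1 − 0.30·exp(1.96 × 0.271) = 49.0%.
- z is 4.14 and 4.44, so p < 0.0001 both ways.

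**Where the conclusion could change.** Take placebo 4%, r = 0.52 and the same sample sizes.

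- 10% dropout, imputed: RR = 0.9 × 0.52 + 0.1 = 0.568, SE 0.307, z = −1.85, p = 0.065.
- 10% dropout, unimputed: RR = 0.52, SE 0.331, z = −1.98, p = 0.048.
- 5% dropout: p = 0.049 imputed and 0.042 unimputed, both significant.

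Solving each formula for p = 0.05 at 4% incidence and 10% dropout, the two analyses disagree only for r of about 0.495 to 0.523. At 8% incidence the corresponding window is about 0.632 to 0.652.

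**Unequal dropout, r = 0.30, dropouts kept as non-events.**

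- 10% MEDI8897, 5% placebo: imputed 63.0%; unimputed 1 − 0.30 × 0.90/0.95 = 71.6%.
- 2% MEDI8897, 10% placebo: imputed 68.6%; unimputed 1 − 0.30 × 0.98/0.90 = 67.3%. The direction reverses.

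**Simulation.** 1,500 trials per case, 1,000 and 500 infants, 8% placebo, assumed stratum weights, 20 imputations at one overall placebo rate. Shares of trials significant in favour of MEDI8897:

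| True RRR | Dropout, MEDI8897 / placebo | Unimputed | Imputed |
|---|---|---|---|
| 70% | 5% / 5% | 99.5% | 99.3% |
| 70% | 10% / 10% | 99.4% | 98.9% |
| 40% | 10% / 10% | 65% | 55% |
| 0 | 5% / 5% | 3.8% | 2.6% |
| 0 | 10% / 10% | 2.7% | 1.3% |
| 0 | 15% / 5% | 7.8% | 0.9% |

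At the nominal 2.5% per direction, the simulation standard error is √(0.025 × 0.975/1,500) = 0.4 points.

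**The case against.** Section 3.5.1.3 speaks of the primary analysis in general, and 3.5.1.4 describes the CMH test as a key secondary analysis. A reader could hold that 3.5.1.3 takes over once the CMH test is promoted. That is arguable, but 3.5.1.3 gives steps only for the Poisson model, and 3.5.1.2 points explicitly to 3.5.1.4. The text is at best contradictory.

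The SAP also has safeguards. Sensitivity analysis 7 imputes at one, two and three times the placebo rate with an exact conditional method that needs no Poisson convergence, so a placebo-rate-imputed estimate would be reported whichever model is primary. Sensitivity analysis 1 already plans the unimputed Poisson result. Both points stand and limit the harm, but neither supplies the primary p-value.

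Three stronger readings are tempting and not supported:

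- **The sponsor could switch after seeing the results.** Stratum size is a baseline count that needs neither outcomes nor treatment codes. The gap is that no threshold or timing is written down.
- **Only placebo dropouts would be imputed, because the sentence names only treated infants.** No section says so. The wording is carried over from version 4, where it followed a reference to the Poisson imputation plan, which covers both arms; version 5 says there is no imputation.
- **The switch always favours MEDI8897.** The unequal-dropout case above shows otherwise.

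**Conclusion.** Wrong as written; should be fixed. The fallback primary analysis uses a missing-data rule that contradicts Protocol 4.8.3.1 and SAP 3.5.1.3, and its stratum-size trigger is undefined.

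Under the planning assumptions and equal dropout of 3% to 10%, the estimated relative risk reduction would be about 2 to 7 points higher than under the required rule (70.0 − 67.9 = 2.1; 70.0 − 63.0 = 7.0). A reader might infer that the switch alone is likely to decide the trial. It is not at the planned effect: it matters only for results close to the significance boundary, in the narrow windows of relative risk shown above. The large excess of false wins in simulation needs dropout on MEDI8897 three times that on placebo.

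The expected values are exact given the formulas. The dropout rates, the 969/484 split and the simulation's stratum weights are assumptions. With a five-parameter model and about 1,453 infants, the fallback may well never be used.

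**What to change.** - **SAP 3.5.1.2 and 3.5.1.3.** State that when the CMH test serves as the primary analysis it is run on the 20 placebo-rate-imputed datasets, with dropouts in both arms imputed, and pooled as in version 4 (log relative risk through MIANALYZE, Wilson-Hilferty for the p-value).
- **If the imputation model fails too.** Sparse events that defeat the Poisson model may also defeat the stratified logistic imputation. In that case use the unstratified Bernoulli placebo-rate imputation already used in 3.5.2.3 and 3.5.1.6.
- **Trigger.** Either make documented non-convergence the only trigger, or set a numeric stratum threshold that is assessed blinded and recorded before unblinding.
- **SAP 3.5.1.4.** Keep the unimputed CMH test as a sensitivity analysis only. State that dropouts are handled identically in both arms and whether they count as non-events or are excluded. Correct MEDI9987.

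The cost is SAP wording; version 4 already specified the pooling method. The fallback estimate becomes slightly less favourable to MEDI8897 in most dropout patterns.
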